## **12. ETHICAL CONSIDERATIONS**

### **12.1. INDEPENDENT ETHICS COMMITTEE**

Not applicable

### **12.2. PATIENT INFORMATION**

Patients will be fully and fairly informed, in comprehensible terms, of the objectives of the study and the nature of the information collected, and of their right to object at any time to the use of the data collected. All this information is conveyed orally to patients by the surgeon. This oral information is completed by an information note given to each patient. Finally, general information on research activities is displayed at the Médipôle de Savoie Hospital.

### **12.3. SUPPORT FOR STUDY**

This is a retrospective observational cohort study, whose only workload is the extraction of data from patient files. The cost of this work will be covered by the contract between the sponsor and the investigator once it has been approved by the CNOM.

## **13. DATA PROCESSING AND STORAGE OF DOCUMENTS AND DATA RELATING TO THE STUDY**

### **13.1. DATA ENTRY AND PROCESSING**

The data will be extracted into a spreadsheet by the investigator himself or his team in the institution. Analysis will be carried out by [name] See paragraph 10.7.

### **13.2. CNIL**

This is a retrospective, single-center observational study. Thus, the study complies with the Reference Methodology MR003 and has been declared to the CNIL.

### **13.3. ARCHIVING**

The archiving of the documents mentioned below is the responsibility of DEDIENNE SANTE SAS. The documentation will be archived for a period of 30 years following withdrawal of the product from the market as defined in quality procedure PRO\_QUAL\_001.

These documents are:

- Protocol et annexes, any amendments
- Information forms
- Database transferred by the investigator
- Follow-up documents
- Statistical report and any files used to produce the report
- Final study report

No displacement or destruction may be carried out without the agreement of the sponsor. At the end of the 30 years, the sponsor will be consulted for destruction. All data, documents and reports may be subject to audit or inspection.

## **14. COMMUNICATION – PUBLICATION RULES**

Data will only be disclosed with the prior joint agreement of the investigator and the sponsor. The results may be communicated and published.

---

 Official text: Deliberation no. 2016-263 of 21 July 2016 approving a reference methodology for the processing of personal data implemented in the context of research in the field of health that does not require the express or written consent of the data subject (MR-003).

*Website consulted:*

<https://www.legifrance.gouv.fr/affichTexte.do?cidTexte=JORFTEXT000033028290&dateTexte=&categorieLien=id>

---

## **15. INVESTIGATOR CONTRACT**

See Annex 5

## **16. LIST OF ANNEXES**

Annex 1: Copy of CE mark and generic reimbursement code applicable to the patients included in the study

Annex 2: List of study variables

Annex 3: Information note and collection of non-opposition form

Annex 4: CNIL registration

Annex 5: Investigator contract

## **17. ASSOCIATED DOCUMENTS**

Information note

---

**Annex 1: Copy of CE mark and generic reimbursement code applicable to the patients included in the study.**

These products are currently supported under the following generic descriptions:

- SYMBOL CUP DM CEM: 3150450 – hip, standard cup, modular, metal-back, without insert, cemented
- SYMBOL CUP DMR HA: 3168042 - hip, reconstruction cup, modular, metal-back, without insert, uncemented
- DUAL MOBILITY PE LINER: 3161130 – hip, solid polymer insert

Le progrès, une passion à partager

Certification  
Médical-Santé

Notified Body N° 0459

**ATTESTATION / CERTIFICATE N° 27262 rev. 5**

Délivrée à Paris le 01 septembre 2015

Issued in Paris on September 1st, 2015

**ATTESTATION CE / EC CERTIFICATE**

Examen CE de la Conception (du produit) / EC Design Examination (of the product)

ANNEXE II point 4 de la directive 93/42/CEE relative aux dispositifs médicaux

**Addendum of the certificate n° 27262 rev.5**  
**Dossiers / Files N° P122250 – P133684 –P137437 – P141487**

**Identification des dispositifs / Identification of devices**

Cotyle double mobilité non cimenté, en chrome-cobalt (ISO 5832-4) revêtu Ti+HAP				Cotyle double mobilité cimenté, en chrome-cobalt (ISO 5832-4)	
SYMBOL CUP DM HA		SYMBOL CUP DMR HA		SYMBOL CUP DM CEM	
Metal-back standard, Ø 44 à Ø 68		Metal-back avec patte et trous pour plots, Ø 44 à Ø 68		Metal-back standard, Ø 44 à Ø 68	
Taille 44	3700502203530	Taille 44	3700502204087	Taille 44	3700502203646
Taille 46	3700502203547	Taille 46	3700502204094	Taille 46	3700502203653
Taille 48	3700502203554	Taille 48	3700502204100	Taille 48	3700502203660
Taille 50	3700502203561	Taille 50	3700502204117	Taille 50	3700502203677
Taille 52	3700502203578	Taille 52	3700502204124	Taille 52	3700502203684
Taille 54	3700502203585	Taille 54	3700502204131	Taille 54	3700502203691
Taille 56	3700502203592	Taille 56	3700502204148	Taille 56	3700502203707
Taille 58	3700502203608	Taille 58	3700502204155	Taille 58	3700502203714
Taille 60	3700502203615	Taille 60	3700502204162	Taille 60	3700502203721
Taille 62	3700502203622	Taille 62	3700502204179	Taille 62	3700502203738
Taille 64	3700502203639	Taille 64	3700502204186	Taille 64	3700502203745
Taille 66	3700502204957	Taille 66	3700502204193	Taille 66	3700502204971
Taille 68	3700502204964	Taille 68	3700502204209	Taille 68	3700502204988
GMDN code : 43167 (acetabular shell)					

LNE/G-MED **0459**

On behalf of the Certification Director  

**Addendum of the certificate n° 27262 rev.5**  
**Dossiers / Files N° P122250 – P133684 – P137437 – P141487**

Insert DUAL MOBILITY PE LINER			
En UHMWPE (ISO 5834-2) pour cotyle double mobilité SYMBOL CUP DM			
Insert pour tête Ø 22.2 Ø44 à Ø68		Insert pour tête Ø 28 Ø46 à Ø68	
Taille 44	3700502203752	-	-
Taille 46	3700502203769	Taille 46	3700502203868
Taille 48	3700502203776	Taille 48	3700502203875
Taille 50	3700502203783	Taille 50	3700502203882
Taille 52	3700502203790	Taille 52	3700502203899
Taille 54	3700502203806	Taille 54	3700502203905
Taille 56	3700502203813	Taille 56	3700502203912
Taille 58	3700502203820	Taille 58	3700502203929
Taille 60	3700502203837	Taille 60	3700502203936
Taille 62	3700502203844	Taille 62	3700502203943
Taille 64	3700502203851	Taille 64	3700502203950
Taille 66	3700502203967	Taille 66	3700502203981
Taille 68	3700502203974	Taille 68	3700502203998
GMDN code : 43168 (non-constrained polyethylene acetabular liner)			

**Annex 2: List of study variables**
**DATA FROM THE COHORT SYMBOL CUP DMR HA AND SYMBOL CUP DM CEM**

PREOPERATIVE DEMOGRAPHICS	Order number of the surgery with this type of implant
	Type of implant DMR HA or CEM
	Month/year of birth
	Sex
	Surgeon identification
	Date of preoperative visit
	Height (cm)
	Weight (Kg)
	BMI
	BMI class
	Operated side
	Etiology / diagnosis
	Medication
	Medication - Specify
	Medical history
	Medical history - Specify
	Local surgical history on the affected hip
	Local surgical history on the affected hip - Specify
	Surgeon's comments
PREOPERATIVE DEVANE & CHARNLEY CLASSIFICATIONS	DEVANE
	CHARNLEY
HHS PAIN	Pain
HHS FUNCTIONAL ABILITIES - WALKING	Lameness
	Support
	Walking perimeter
HHS FUNCTIONAL ABILITIES – DAILY LIFE	Socks and shoes
	Stairs
	Sitting position
	Public transport
HHS – MOBILITY	Flexion °
	Extension °
	Abduction °
	Adduction °
	External rotation °

	Internal rotation °
	TOTAL MOBILITY
DEFORMATIONS	LLI (cm)
	Flessum °
	Adductum °
	Internal rotation °
	TOTAL DEFORMATIONS
	TOTAL PREOPERATIVE HHS
SURGICAL INTERVENTION	Date of surgery
	Age at surgery
	Intervention duration (min)
	Surgical approach
	Type of intervention
	Surgeon's comments
	Operative adverse events
ACETABULAR COMPONENTS	Cup walls
	Fragile acetabulum zone
	Cup identification
	Size
	Cement
	Reaming diameter
	Liner
	Femoral head
	Diameter
	Bone graft
	Screw
	Pegs
	Associated surgical procedure
FEMORAL STEM	Stem identification
	Cement
	CCD angle
	Collar
	Broach size
	Stem size
	Neck length
	Bone graft
STABILITY	Stability of the hip
INCIDENTS	Operative adverse events
SURGEON'S COMMENTS – END OF SURGERY	Surgeon's comments
1-year postoperative assessment	Date
	Death

	Reason for death
1-year postoperative assessment	
DEVANE & CHARNLEY	DEVANE
CLASSIFICATIONS	CHARNLEY
HHS PAIN	Pain
HHS FUNCTIONAL ABILITIES - WALKING	Lameness
	Support
	Walking perimeter
HHS FUNCTIONAL ABILITIES – DAILY LIFE	Socks and shoes
	Stairs
	Sitting position
	Public transport
HHS – MOBILITY	Flexion °
	Extension °
	Abduction °
	Adduction °
	External rotation °
	Internal rotation °
	TOTAL MOBILITY
DEFORMATIONS	LLI (cm)
	Flessum °
	Adductum °
	Internal rotation °
	TOTAL DEFORMATIONS
	TOTAL 1-YEAR FU HHS
Adverse events and reason	Adverse events at 1-year FU
	Date of occurrence of the adverse event
	Potential reason
Treatment	Without revision surgery
	Surgical revision without component revision
	Surgical revision with revision of components
	Date of revision surgery
	Adverse event solved Yes/No
	Unsolved adverse event – reason
Radiologic assessment at 1 year	Global offset
	Global length
	Cup
	Cup inclination
	Face stem

	Profile stem
	Surgeon's comments
2-year postoperative assessment	Date of telephone interview
	Death
	Reason for death
2-year postoperative assessment DEVANE & CHARNLEY CLASSIFICATIONS	DEVANE
	CHARNLEY
HHS PAIN	Pain
HHS FUNCTIONAL ABILITIES - WALKING	Lameness
	Support
	Walking perimeter
HHS FUNCTIONAL ABILITIES – DAILY LIFE	Socks and shoes
	Stairs
	Sitting position
	Public transport
HHS FUNCTIONAL ABILITIES TOTAL	HHS FUNCTIONAL ABILITIES TOTAL AT 2-YEAR FU
Adverse events and reason	Adverse events at 2-year FU
	Date of occurrence of the adverse event
	Potential reason
Treatment	Without revision surgery
	Surgical revision without component revision
	Surgical revision with revision of components
	Date of revision surgery
	Adverse event solved Yes/No
	Unsolved adverse event – reason

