PROVISIONAL STUDY TIMETABLE	
CPP notice: N.A.  CEREEs notice: N.A.  CNIL receipt: 2176595  Start of the study: As soon as CNIL receipt is received.  Duration of inclusion period/data collection: N.A. given retrospective nature  Duration of participation of each subject: N.A. given retrospective nature  Anticipated end of study: N.A. given retrospective nature  End-of-study report: Within 30 days of start of study

STATISTICAL DATA ANALYSIS	
 
- Descriptive statistics: preoperative, operative, postoperative
 
- Tabulation of adverse events
 
- Kaplan-Meier analysis of implant survival
 
- Comparison tests of preoperative versus 1-year and 2-year postoperative efficacy scores.
 

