## **5. STUDY FEASABILITY**

The clinical research associate (CRA) delegated by the sponsor will make two or three visits to the investigational center:

- An inclusion visit to confirm the investigator's adherence to the protocol and to define the procedures for extracting and transferring anonymized data from the electronic patient record management system. As this is a single-center study, this visit will take place before the protocol is submitted to the CNIL.
- A visit to extract and transfer anonymized data from patient files, and to call patients to obtain their two-year follow-up data. On this occasion, patients will be informed that they may object to the inclusion of their information in this study. During this visit, the sponsor's clinical research associate will check that the data are consistent with the contents of the patient files. He/she will confirm the completeness of the cohort, with consecutive placement of dual-mobility acetabular implants. An anonymized list of all THA during the recruitment period will be obtained and checked to establish the sampling frame. This visit will take place at the start of the study.
- An additional visit by the CRA, to obtain missing data and resolve discrepancies, will take place if necessary.

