## **6. RÉALISATION PRATIQUE DU PROTOCOLE.**

### **6.1. DÉROULEMENT DES VISITES LIÉES A L'ÉTUDE**

The clinical research associate (CRA) delegated by the sponsor will make two or three visits to the investigational center:

- An inclusion visit to confirm the investigator's adherence to the protocol and to define the procedures for extracting and transferring anonymized data from the electronic patient record management system. As this is a single-center study, this visit will take place before the protocol is submitted to the CNIL.
- A visit to extract and transfer anonymized data from patient files, and to call patients to obtain their two-year follow-up data. On this occasion, patients will be informed that they may object to the inclusion of their information in this study. During this visit, the sponsor's clinical research associate will check that the data are consistent with the contents of the patient files. He/she will confirm the completeness of the cohort, with consecutive placement of dual-mobility acetabular implants. An anonymized list of all THA during the recruitment period will be obtained and checked to establish the sampling frame. This visit will take place at the start of the study.

- An additional visit by the CRA, to obtain missing data and resolve discrepancies, will take place if necessary.

In the event of death reported by the patient's entourage without a date, the surgeon will question the civil registry of the patient's commune of birth to obtain the date and cause of death.

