## **6.3. DESCRIPTION OF THE GENERAL LOGISTICAL ORGANIZATION OF THE STUDY**

The registered protocol and the copy of the database will be produced in 3 copies:

- The first to the investigator
- The second to the sponsor
- The third to the statistician.

All exchanges will be made by written mail transfer and USB key with acknowledgement of receipt. Any question raised by the statistician will be forwarded to the sponsor, who will obtain the investigator answer.

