## **9. DATA COLLECTED**

The data is collected in the electronic patient record management system will be copied directly into a spreadsheet by the surgeon or on site by the CRA. 2-year follow-up data will be entered directly into the spreadsheet. The list of variables is in Annex 2.

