**2176595 v 0**

du 25 avril 2018

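### Does the missing date-of-death field in Annex 2 leave the primary Kaplan-Meier analysis without a censoring date for second-year deaths?

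*Combined protocol and SAP*

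**What the plan says.** Section 3.2 defines the primary endpoint as implant survival at 2 years in the living patient. Only revision surgery with removal of the implant counts as an event. Section 10.3 names a Kaplan-Meier analysis and adds nothing about censoring.

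Section 9 says of the study spreadsheet: "The list of variables is in Annex 2". For the 1-year and the 2-year assessment, Annex 2 has an entry for death and one for "Reason for death", but none for when the patient died. The 2-year block opens with "Date of telephone interview". It also lists a date for adverse events and a date for revision surgery.

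Section 6.1 covers a death that the family reports without a date: the surgeon asks the civil registry "to obtain the date and cause of death". Section 10.6 puts the mid-month date in place of a missing day in adverse-event and follow-up dates.

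**The concern.** The plan goes to the civil registry for a date and then lists nowhere to store it, although the cause of death has its own field. The primary analysis needs that date: a patient who dies with the implant in place should leave the risk set on the day of death.

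The listed dates are poor substitutes. The interview date falls after 24 months, so a second-year death would count as at risk for the whole period and survival could come out too high. The 1-year visit date takes the patient out too early, so survival could come out too low. The adverse-event date would serve only if death were also entered as an adverse event, which the protocol does not say. At stake is the primary estimate, which section 2.2 intends for CE-mark renewal and a reimbursement application.

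**Working it through.** **Timing of the interview**

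- Latest eligible surgery: section 7.1 requires 2 years of follow-up by 1 March 2018. Read as elapsed time, this means surgery on or before 1 March 2016.
- Start of study: the summary's timetable says "As soon as CNIL receipt is received", and the receipt in Annex 4 is dated "du 25 avril 2018".
- Calls: section 5 has the clinical research associate visit at the start of the study and "call patients to obtain their two-year follow-up data".
- 1 March 2016 to 25 April 2018 is 785 days, and 785 / 30.4375 = 25.8 months.

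So every call made for the study falls after month 24. This does not cover every 2-year record. The summary uses the interview only where the medical file is incomplete, and section 6.2 describes repeat calls as usual practice, so an earlier routine contact may already be on file.

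**Effect on the primary estimate**

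The plan gives no expected number of deaths or revisions and no precision figure behind its minimum of 20, so there is no planned value to reproduce. The counts below are assumptions. Take n = 20, *d* deaths at month 14 and *r* revisions with removal at month 18.

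- Deaths censored on the true date: S(24) = 1 − r/(20 − d)
- Deaths dated by the interview: S(24) = 1 − r/20

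| d | r | True date | Interview date | Shift (points) |
|---|---|---|---|---|
| 1 | 1 | 1 − 1/19 = 0.9474 | 0.950 | +0.26 |
| 2 | 1 | 1 − 1/18 = 0.9444 | 0.950 | +0.56 |
| 4 | 1 | 1 − 1/16 = 0.9375 | 0.950 | +1.25 |
| 1 | 2 | 1 − 2/19 = 0.8947 | 0.900 | +0.53 |
| 2 | 2 | 1 − 2/18 = 0.8889 | 0.900 | +1.11 |
| 4 | 2 | 1 − 2/16 = 0.8750 | 0.900 | +2.50 |

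If the deaths are truly at month 20 but dated at the 1-year visit, the two columns change places and the shifts keep their size with a minus sign. With no revision in the affected window, the shift is 0. At n = 40 the range is from (1 − 1/40) − (1 − 1/39) = +0.06 points to (1 − 2/40) − (1 − 2/36) = +0.56 points.

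The number at risk at month 24 is overstated by *d*. With d = 2 and r = 1 it is 20 − 1 = 19 instead of 20 − 2 − 1 = 17.

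**Comparison with sampling error**

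For d = 2 and r = 1, the Greenwood log-log 95% interval is 66.6% to 99.2%, a width of 32.6 points against a shift of 0.56. For the worst row, the exact 95% interval for 18 of 20 is 68.3% to 98.8%, a width of 30.5 points against a shift of 2.5.

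**Does any stated rule produce the wrong date?**

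No. Section 10.3 does not tell the analyst to censor at the interview. Section 3.2, with removal as the only event and survival defined in the living patient, points to death as the exit time. Under section 6.1 the surgeon has the date either from the family or from the registry.

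**The case for a change.** The best argument for a change is that it costs almost nothing and concerns the primary result. The date is already being sought, so one more column and one sentence on censoring would settle the matter before extraction. Leaving it to a query is less comfortable than it sounds. Section 6.3 says "Any question raised by the statistician will be forwarded to the sponsor", exchanges go by post and USB key, and the summary wants the report within 30 days of study start. A registry request raised only at analysis would fit that schedule badly.

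The omission does stand: neither the Annex 2 field nor the censoring sentence exists, and the adverse-event date is not an assured home for a date of death. The schedule argument is weaker. Section 6.1 places the registry request within data collection, so a later query would ask only for a date the surgeon should already hold. Sections 5 and 6.1 also provide an extra visit for missing data and discrepancies. The investigator contract in Annex 5 refers to case report forms that are not reproduced in the text, so Annex 2 may not show the full layout of what is captured.

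The upper end of the size range is also a constructed extreme. It needs 4 of 20 patients to die in the second year, with every death on the unfavourable side of every revision. Nothing in the documents supports such counts.

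**Conclusion.** The gap is real but does not call for a change. The plan obtains the date of death and defines the endpoint so that death with the implant in place ends observation. No instruction leads to a wrong date, and a death flag with no date beside it is something a statistician running a Kaplan-Meier analysis would query as a matter of course.

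If it were mishandled all the same, the error would be 0 without a revision in the affected window and otherwise about 0.3 to 2.5 points in either direction at n = 20. That rests on assumed counts of 1 to 4 deaths and 1 or 2 revisions, on the elapsed-time reading of section 7.1, and on calls made for the study. It is small beside a 95% interval about 30 points wide. Section 2.3 sets no hypothesis or threshold that such a shift could cross. The likely cost is one late query or a slightly wrong number at risk, and a wrong conclusion about the implants is unlikely.

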**RÉCÉPISSÉ**

**DÉCLARATION DE CONFORMITÉ À  
UNE MÉTHODOLOGIE DE  
RÉFÉRENCE**

Numéro de déclaration  
**2176595 v 0**

du 25 avril 2018

**A LIRE IMPÉRATIVEMENT**  
La délivrance de ce récépissé atteste que vous avez transmis à la CNIL un dossier de déclaration formellement complet. Vous pouvez désormais mettre en oeuvre votre traitement de données à caractère personnel.  
La CNIL peut à tout moment vérifier, par courrier, par la voie d'un contrôle sur place ou en ligne, que ce traitement respecte l'ensemble des dispositions de la loi du 6 janvier 1978 modifiée en 2004. Afin d'être conforme à la loi, vous êtes tenu de respecter tout au long de votre traitement les obligations prévues et notamment :  
1) La définition et le respect de la finalité du traitement,  
2) La pertinence des données traitées,  
3) La conservation pendant une durée limitée des données,  
4) La sécurité et la confidentialité des données,  
5) Le respect des droits des intéressés : information sur leur droit d'accès, de rectification et d'opposition.  
Pour plus de détails sur les obligations prévues par la loi « Informatique et libertés », consultez le site Internet de la CNIL : [www.cnil.fr](http://www.cnil.fr).

**Annex 5. Investigator contract****PROJET DE CONVENTION**

**Selon article L.4113-6, loi N° 2007-248 du 26 février 2007**

**- Préalablement à la présente convention, il est rappelé ce qui suit :**

" - Est interdit le fait, pour les membres des professions médicales visées au titre 1er du livre IV du code de la santé publique, de recevoir des avantages en nature ou en espèces, sous quelque forme que ce soit, d'une façon directe ou indirecte, procurés par des entreprises assurant des prestations, produisant ou commercialisant des produits pris en charge par des régimes obligatoires de sécurité sociale.

- Toutefois, l'alinéa précédent ne s'applique pas aux avantages prévus par conventions passées entre les membres de ces professions médicales et des entreprises dès lors que ces conventions ont pour objet explicite et but réel des activités de recherche ou d'évaluation scientifique, qu'elles sont, avant leur mise en application, soumises pour avis au Conseil Départemental de l'Ordre des Médecins et notifiées lorsque les activités de recherche ou d'évaluation sont effectuées même partiellement, dans un établissement de santé, au responsable de l'établissement, et que les rémunérations ne sont pas calculées de manière proportionnelle au nombre de prestations ou produits prescrits, commercialisés ou assurés. "

*Extrait de l'article L4113-6 du code de la santé publique.*

